8.2 Sample size and randomization

The primary outcome for this study is PHQ-9 utilization. Assuming 75% PHQ-9 utilization prior to implementation of the Pathway Platform and 90% PHQ-9 utilization after implementation of the Pathway Platform, we will need 100 patients per group, for a total of 200 patients, assuming 80% power and a 2-sided alpha of 0.05 using Pearson chi square test for two independent proportions. To allow for subgroup analyses the sample will include 200 patients per group, for a total of 400 patients; 200 patients will comprise the “post-implementation” cohort and 200 will comprise the “pre-implementation” cohort. **Table 2** presents additional sample size calculations based on different assumptions of PHQ-9 utilization.

Table 2: Sample size calculations based on different assumptions of PHQ-9 utilization, alpha = 0.05, Power = 80%.
--

PHQ-9 utilization pre-implementation	PHQ-9 in Pathway post-implementation	N patients per group
75%	80%	1,094 per group
75%	90%	100 per group
75%	95%	49 per group
50%	65%	170 per group
50%	80%	30 per group
50%	90%	20 per group

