8.3 Outcomes

8.3.1 Primary outcome

The primary process outcome is PHQ-9 utilization over a six-month period. For purposes of this study, PHQ-9 utilization will be defined as documentation of at least 2 PHQ-9 scores in the EMR over the initial 6-month study period. The proportion of patients who meet this definition will be compared between patients attending clinics pre- and post- implementation of the Pathway Platform. Additional analyses exploring the number of PHQ-9s over the study period will also be conducted.

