8.3.2 Secondary outcome

Process outcomes: The following secondary process outcomes will be compared between patients attending clinics pre- and post- implementation of the Pathway Platform.

- Measurement- based care: The proportion of patients reflecting measurement-based care informed MDD treatment adjustments in their charts, defined as at least one dose change, medication switch, or add on medication during the study period. The frequency and types of treatment adjustments will also be explored.
- Shared- decision making: The proportion of patients reflecting shared-decision making, using the OPTION12 Tool framework.²⁶ The tool will be modified by adding a thirteenth domain inquiring about goal setting (Asking the patient or caregiver about goals of treatment). The frequency and domains of shared-decision making will also be explored in a manual chart review and a variable added to assess if the clinician documented asking the patient about their goals of treatment.
- Referrals to behavioral health: The proportion of patients with at least one referral will be compared. The frequency and types of referrals will also be explored.
- Follow-up after hospitalization for mental illness: The proportion of hospitalized adults who receive follow-up within 7 days of discharge and within 30 days of discharge.
- Follow-up after emergency department visit for mental illness: The proportion of adults

who receive follow-up within 7 days of discharge and within 30 days of ED visit.

- Healthcare resource utilization: Number and costs associated with hospital admission, length of stay, emergency room admissions, and encounters with outpatient clinics. Costs will be calculated using USA national average costs for inpatient and outpatient visits or using an average Advocate Health Care system cost.

Patient clinical outcomes: The following outcomes will be compared between patients attending clinics pre- and post- implementation of the Pathway Platform, keeping in mind that the number of patients with these measures in the pre- implementation patient group will be limited:

- MDD remission: The proportion of patients with PHQ-9 ≤ 5 at the end of the study period. The last measurement available during the study period will be used to calculate remission.
- MDD response: The proportion of patients with a 50% or greater reduction in PHQ-9 scores. The first and last scores available during the study period will be used to calculate response.

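### Response can be classified essentially only in patients who meet the primary endpoint, so the pre/post response test depends on who was measured; remission has a weaker form of the same dependence

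*Combined protocol and SAP*

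**What the plan says.** Section 8.3.1 sets the primary endpoint: "PHQ-9 utilization will be defined as documentation of at least 2 PHQ-9 scores in the EMR over the initial 6-month study period". Section 8.2 sizes the study on a rise in that share: "Assuming 75% PHQ-9 utilization prior to implementation of the Pathway Platform and 90% PHQ-9 utilization after implementation of the Pathway Platform".

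Section 8.3.2 then lists remission and response as clinical outcomes to be compared between cohorts. For response, "The first and last scores available during the study period will be used to calculate response". For remission, "The last measurement available during the study period will be used to calculate remission". The only caution is "keeping in mind that the number of patients with these measures in the pre- implementation patient group will be limited".

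Section 8.4 places patient clinical outcomes under primary and secondary hypothesis testing, and compares categorical outcomes by Pearson chi-square at two-sided p < 0.05. Neither section gives a denominator for response or remission, a rule for patients with no score or one score, an adjustment, or a sensitivity analysis.

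Sections 4.4.1 and 4.4.2 explain why measurement will differ. In the post-implementation cohort the app prompts a PHQ-9 every two weeks and sends it to the EMR. The pre-implementation cohort has only what routine care recorded.

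**The concern.** A first and a last score that can show change exist only if the patient has at least two PHQ-9s. Apart from small differences in data source, such as an app score that never reached the EMR, the patients who can be classified for response are those who meet the primary endpoint. The Platform is designed to enlarge that group, so success on the primary endpoint changes who enters the response comparison.

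The plan treats the shortage of pre-implementation scores as one of numbers. It is also one of selection: pre-implementation patients are those whom routine care chose to re-measure, and post-implementation patients are largely those who answered prompts. A chi-square on such groups can show a difference that reflects measurement, or hide a real one.

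For remission the link is looser, because one PHQ-9 is enough. Even one is not guaranteed, however: sections 4.1 and 4.2 allow entry on a PHQ-2 alone.

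At stake is the secondary objective in section 1.2, which asks whether the Platform improves response and remission.

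**Working it through.** **Inputs from the documents.** 200 patients per cohort; shares with at least two scores m₁ = 0.75 (pre) and m₂ = 0.90 (post); Pearson chi-square, two-sided alpha 0.05 (section 8.2).

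**Assumptions, not in the documents.** True response R = 40% in both cohorts, so no true effect. The gap g is the response rate in unmeasured patients minus that in measured patients.

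**The plan's own figure.** n = [1.960·√(2·0.825·0.175) + 0.842·√(0.75·0.25 + 0.90·0.10)]² / 0.15² = 99.5, rounded up to 100 per group. This agrees with section 8.2.

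**Who can be classified for response.** Pre 0.75 × 200 = 150; post 0.90 × 200 = 180. So 25% and 10% have no observable response.

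**False-positive rate.** With observed proportions p₁ and p₂, d = p₂ − p₁, and pooled and unpooled standard errors s₀ and s₁: 1 − Φ((1.96·s₀ − d)/s₁) + Φ((−1.96·s₀ − d)/s₁).

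**Denominator 1: measured patients only (150 and 180).** From R = m·r + (1 − m)(r + g), the observed rate is r = R − (1 − m)g, and the spurious difference is g(m₂ − m₁) = 0.15g.

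| Gap g, both cohorts | Pre | Post | Difference | False positives |
|---|---|---|---|---|
| 10 points | 37.5% | 39.0% | 1.5 points | about 6% |
| 20 points | 35.0% | 38.0% | 3.0 points | about 9% |
| 32 points | 32.0% | 36.8% | 4.8 points | about 15% |

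For g = 20 points: s₀ = 0.0533, s₁ = 0.0532, d = 0.03, giving 0.087. Reversing the sign of g reverses the difference and leaves the false-positive rates almost unchanged.

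A 32-point gap arises if 60% of pre-implementation responders and 85% of non-responders are re-measured. Measured share: 0.4·0.60 + 0.6·0.85 = 0.75. Response in the measured: 0.24/0.75 = 32%. Response in the unmeasured: 0.16/0.25 = 64%. If the gap exists in the pre-implementation cohort only, the comparison is 32% of 150 versus 40% of 180, and the false-positive rate is about 32%.

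**Denominator 2: all 200, unmeasured counted as non-responders.** Taking measured patients as representative, the observed rates are 0.75·0.40 = 30% and 0.90·0.40 = 36%. The difference is 0.15R, positive at any response rate. The false-positive rate is about 25% (18% at R = 30%, 33% at R = 50%).

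**Bounds.** Suppose measured patients show 40% in both cohorts.
- Pre: from 0.75·0.40 = 0.30 to 0.30 + 0.25 = 0.55.
- Post: from 0.90·0.40 = 0.36 to 0.36 + 0.10 = 0.46.
- True difference, post minus pre: from 0.36 − 0.55 = −0.19 to 0.46 − 0.30 = +0.16.

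**Remission.** No figure can be computed. The 75% and 90% are shares with at least two scores, and the documents give no share with at least one.

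**The case against.** The sponsor can fairly say that these are secondary outcomes, that the thin pre-implementation data are acknowledged, and that section 1.2 sets out to determine whether outcomes improve and does not claim that they do. It can add that the wording about patients who have these measures points to an analysis of measured patients, where bias arises only if measured and unmeasured patients differ and is modest at 75% versus 90%. All of this stands. It limits the size of the problem but does not remove it: the denominator is still unstated, the acknowledgement leads to no rule, and section 8.4 still puts the comparison under hypothesis testing.

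Three stronger readings are tempting and should not be drawn.

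- A reader might infer that remission is also tied to the primary endpoint. It is not; section 8.3.2 needs only one score.
- A reader might take the 32% false-positive rate as the expected size. It needs a 32-point gap in one cohort and none in the other, although answering app prompts is itself selective. The documents give no gap at all.
- A reader might infer that the bias must favour the Platform. That follows only if unmeasured patients count as non-responders, which is the less likely reading of section 8.3.2.

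**Conclusion.** The concern holds for response and, in a weaker and unquantified form, for remission. Whichever denominator is used, the planned pre/post response test depends on the measurement rate, which the Platform is meant to change.

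Under the likelier measured-only reading the distortion at 75% versus 90% is modest, of unknown direction, and nil if measured and unmeasured patients respond alike. Counting unmeasured patients as non-responders is worse and one-sided. The bounds make the same point without any selection model: equal observed rates of 40% would be compatible with a true difference anywhere from −19 to +16 points.

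These sizes rest on the assumed response rate and gaps, and on the plan's own measured shares. The primary endpoint analysis is not affected by this point.

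**What to change.** In sections 8.3.2 and 8.4:

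1. Name the denominator for response and for remission, and state how patients with no score or one score are handled.
2. Report the number measured in each cohort, separately for response (two scores) and remission (one score).
3. Show best-case and worst-case bounds, or a tipping-point analysis, beside the chi-square result.
4. Report the pre/post response and remission comparison as descriptive, not as evidence of improvement, unless its conclusion survives step 3.

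Weighting for being measured, using a few baseline variables already collected in both cohorts (for example age, sex and entry severity), can be added as an optional sensitivity analysis. It should not lead. It cannot correct selection on response itself, only about 20 post-implementation patients would be unmeasured on the plan's figures, and entry severity may be a PHQ-2 in some patients and a PHQ-9 in others.

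The cost is SAP wording, a few extra tables and a weaker statement on response and remission. No new data are needed.

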8.3.3 Exploratory outcomes

Patient clinical and reported outcomes:

- The following patient reported outcomes will be collected in the Pathway Platform throughout the study. The difference in scores between the baseline measure, 6-months, and end of the study will be compared. This will be restricted to patients who completed these scales at these two-time points. To be inclusive of all patients, additional analyses will be conducted to compare first and last scores available:
 - PHQ-9
 - WHO-5
 - PDQ-D5

- The following patient reported outcomes will be collected in the Pathway Platform and described at 6-months and end of the study:
 - Antidepressant Medication adherence
 - Antidepressant Medication dose adjustment and switches
 - Side effects
 - Depression remission
 - Depression response
 - Goal attainment
- Patient reported outcomes (PAM-13, CollaboRATE and WSAS) will also be explored at 6 months and end of the study.

Pathway Platform and report utilization: Pathway Platform analytics will be explored to understand patient adherence to the platform which includes frequency of logging into the Pathway Platform and frequency of completing each of the Pathway Platform functionalities. Care-team utilization of Pathway Platform reports will also be explored, including describing type of care team members who viewed the Pathway Platform reports as well as frequency of viewing the reports.

Education utilization: Frequency of viewing material in the resource education center will be described by patient and by care-team members. Commonly viewed educational material will be highlighted.

Subgroup analysis: primary, secondary, and exploratory outcomes will be compared across a number of patient demographic and clinical characteristics, including PHQ-9 severity at baseline, comorbidities (see appendix 3 for comorbid conditions and ICD codes), app utilization by patients, and EMR report utilization by providers. Additional subgroup analysis will be conducted by type of care model at the site level (e.g. collaborative care vs. non collaborative care sites).

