4.4.1 Pathway App

Pathway is a mobile application designed to gather health information related to the management of depression to enhance patient clinical engagement and guide patient care. The patient facing interface includes a digital assistant that allows patients to interact with the Pathway Platform in a chat-based conversational text interface. The information collected from the patient is intended to assist the care team in managing the patient's depression through enhancing measurement-based care and shared-decision making - enhancing patient-provider engagement and ultimately patient outcomes. The study will deploy the most recent iteration of the Pathway Platform. Earlier iterations were piloted in four primary care clinics.¹⁶ Feedback from this pilot was used to enhance Pathway Platform functionality. The current iteration of the Pathway Platform, which is the version that will be used in the implementation study described in this protocol, prompts patients to complete four scales to assess depression status biweekly (Patient Health Questionnaire [PHQ-9] and Perceived Deficits Questionnaire-Depression [PDQ-D5]), quality of life (World Health Organization- Five Well Being Index [WHO-5]), and cognition (Digit Symbol Substitution Test [DSST]).^{7,17,18,19} The Pathway Platform also includes a daily evening check-in with the patient to collect information on medication adherence and side effects. Patients reporting side effects related to sleep are prompted to complete the PROMIS Sleep Disturbance 6a and patients reporting side effects related to sexual dysfunction are prompted to complete the Arizona Sexual Experience Scale (ASEX).^{20,21} An optional functionality of the Pathway Platform is to set and track goals using the Goal Attainment approach adapted for depression during clinic visits with a healthcare provider.²² In addition, the Pathway Platform includes patient facing education for the patient on how to use the Pathway Platform to collect data as well as how to prepare for a visit with health care providers, set and assess progress towards goals and self-management. For purposes of evaluating this implementation study three additional scales assessing patient-provider engagement and functional improvement will be deployed through the Pathway Platform at baseline and subsequently every 6 months until the end of the study (Patient Activation Measure - 13[PAM-13], CollaboRATE, and Work and Social Adjustment Scale [WSAS]).^{23,24,25}

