5. STUDY PROCEDURES

5.1 Schedule of events

Table 1: Schedule of evaluations

	Pre-electronic and manual chart reviews	Complete education by care team	Screening	Baseline assessment	6 month Assessment	Final assessment		
Study Day/Week:		Day -1	Day 0	Day 1	Day 168 - 172 [^]		Study end	
Visit Windows (Days):	Source		EMR/ patient scheduling	Pathway Platform	Pathway Platform	EMR and Manual Review	Pathway Platform	EMR and Manual Review
Patient electronic screening			X					
Informed consent			X					
Onboarding			X					
Demographic characteristics	X							
Number of PHQ-9 scores documented	X			X	X	X	X	
Treatment adjustments	X			X	X	X	X	
Shared decision making (OPTION-12 and CollaboRATE)	X			X	X	X	X	X
Referral to behavioral health	X					X		X
PHQ-9 scores	X			X			X	
Emergency room visits	X					X		X
Emergency room visits due to mental illness	X					X		X
Hospital admissions	X					X		X
Follow up after emergency room and hospital visits	X					X		X
Hospital admissions due to mental illness	X					X		X
Healthcare resource utilization								
Outpatient visits including phone calls	X					X		X
Outpatient visits including phone calls due to mental illness	X					X		X
Remission and response (using PHQ-9 data)	X				X		X	
PAM 13 ***				X	X			X
CollaboRATE**, ***				X	X			X
WSAS ***				X	X			X
PHQ-9				X	X	X	X	X
WHO-5				X	X			X
PDQ-D5				X	X			X
Medication adherence				X	X			X
Side effects				X	X			X
PSD-6 (only if reporting side effects of sleep problems)				X	X			X
ASEX (only if reporting side effects of sexual problems)				X	X			X
Goal Setting				X				
Goal Attainment					X			X
App analytics				X	X			X
Report analytics				X	X			X
Educational material analytics				X	X			X
In depth interviews (Patients and Clinicians)								X
Adverse Events*	X		X	X	X		X	X
Serious Adverse Events	X		X	X	X		X	X

[^]Day 168 reflects end of initial 24 week study period in which the final set of care questionnaires are available for completion (PHQ-9, WHO-5 and PDQ-D5), these expire within 3 days. Day 172; The off-boarding process is available, including the research questions (PAM-13, WSAS,

CollaboRATE), these expire after 30 days.

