- Diagnosis progress notes stating change from mild, moderate, or severe, to in remission or partial remission will be assessed descriptively.

Patient reported outcomes: The difference in scores between baseline, and 6-month follow up will be compared among patients using the Pathway Platform who completed the following measures:

- PAM-13
- CollaboRATE (this questionnaire is also included as a 3-month post-enrollment assessment and will be analyzed across all available time points)
- WSAS

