8.4 Data analysis

For primary and secondary hypothesis testing, process measures, patient clinical outcomes, and health care resource utilization will be compared pre- and post- implementation of the Pathway Platform.

Additional patient reported outcomes will be compared among patients using the Pathway Platform only at baseline and end of study. For pre-implementation, outcomes will be assessed among patients who visited one of the study clinics at least once over the pre-implementation study period and were eligible to use the Pathway Platform, if it had been available. For the post-implementation period, the Pathway Platform will be the data source for paired t-test analysis, assessing change in continuous variables including PHQ-9 scores. Categorical outcomes will be presented as proportions and compared using Pearson Chi2 test. Continuous outcomes will be assessed for normality and presented as means and standard deviations (SD) or medians and interquartile ranges (IQR); continuous outcomes will be compared using Student's t test for independent groups. Two-tailed tests using a significance threshold of $p < 0.05$ will be used for all tests.

Exploratory outcomes: will be described among patients attending the pathway platform clinics only and will be compared between baseline, 6-month and extended follow up. Change in these outcomes overtime, including utilization analytics will also be explored. Categorical outcomes will be presented as proportions and compared using McNemars' test. Continuous outcomes will be assessed for normality and presented as means and standard deviations (SD) or medians and interquartile ranges (IQR); continuous outcomes will be compared using Student's Paired t test for single group comparison. Two-tailed tests using a significance threshold of $p < 0.05$ will be used for all tests. Goal attainment will be summarized by proportion of patients who achieve their identified goals based on the set time bound duration of the goal (i.e., GAS Score ≥ 50).^{29,30} The goal attainment scale adapted for depression yields a norm-based score (standardized to a mean of 50, SD of 10) at baseline and at the end of the time bound goal; the change from score from baseline will also be summarized.

System level performance: Process outcomes will be evaluated at the system level (all primary

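### The 6-month change in PHQ-9, WHO-5 and PDQ-D5 is tested in patients with both scores, with a Day 168 questionnaire open for 3 days; the planned back-up does not estimate a 6-month change, and a repeated-measures model on scores already collected would

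*Combined protocol and SAP*

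**What the plan says.** **App scales.** Section 8.3.3 compares PHQ-9, WHO-5 and PDQ-D5 at baseline, 6 months and end of study, then says: "This will be restricted to patients who completed these scales at these two-time points". The next sentence adds a second analysis: "To be inclusive of all patients, additional analyses will be conducted to compare first and last scores available". For exploratory outcomes Section 8.4 states that "continuous outcomes will be compared using Student's Paired t test for single group comparison", and that change over time will be explored, with no model named. The paragraph of Section 8.4 on primary and secondary testing also names a paired t test, on Platform data, for change in PHQ-9.

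**Timing.** The footnote to Table 1 (Section 5.1) describes Day 168 as the end of the initial 24 weeks, when "the final set of care questionnaires are available for completion (PHQ-9, WHO-5 and PDQ-D5), these expire within 3 days". The app "prompts patients to complete four scales to assess depression status biweekly" (Section 4.4.1), and Section 6.2 also calls the PHQ-9 biweekly. Section 7 lets patients stop using the app whenever they wish.

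**Secondary scales.** For PAM-13, CollaboRATE and WSAS, Section 8.3.2 says: "The difference in scores between baseline, and 6-month follow up will be compared among patients using the Pathway Platform who completed the following measures". It adds that CollaboRATE, also asked at 3 months, will be analysed over every available time point. Section 8.4 says: "Additional patient reported outcomes will be compared among patients using the Pathway Platform only at baseline and end of study". The note to Figure 1 (Section 3.2) puts secondary outcomes at 6 months and leaves later data to exploratory work.

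The plan gives no expected completion rate, missing-data assumption, imputation method or mixed model. It also has no rule on whether a nearby score may stand in for a missed Day 168 score.

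**The concern.** A patient who answers regularly up to week 22 but misses the 3 days after Day 168 has no score at the end point. With no analysis window stated, that patient appears to leave the 6-month contrast, although a dozen scores may be on file. Missing end scores are foreseeable, since app use is voluntary.

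Whether this matters depends on why people stop. If patients who are doing badly stop, those left look better than the cohort; if patients who feel well stop, the reverse. If stopping has nothing to do with the score, the completer mean is right but less precise than it need be.

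The first-versus-last analysis answers a different question. The last score may come from week 2 or week 24, so the result is a change over mixed follow-up. A patient with one score has no change to contribute. If improvement is gradual, early stopping pulls the result towards zero even when stopping is random. The two planned analyses can therefore disagree, and the plan gives no basis for reconciling them.

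**Working it through.** **1. The plan's own figure.** No sample size, SD, power or completion rate is given for the app-scale change. The only sizing (Section 8.2) is for the primary outcome, 75% versus 90%:

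n = [1.960 x sqrt(2 x 0.825 x 0.175) + 0.842 x sqrt(0.75 x 0.25 + 0.90 x 0.10)]^2 / 0.15^2 = (1.053 + 0.443)^2 / 0.0225, which rounds up to 100 per group.

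This reproduces the stated 100 but does not bear on the present point.

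**2. Scores used.** Reading biweekly as every two weeks (an assumption that fits 168 / 14 = 12), there are 12 + 1 = 13 scheduled scores. The paired test uses 2, leaving 11 unused.

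**3. Pairs left out of 200, over an assumed range of completion.** The smallest standardised paired change detectable with 80% power at two-sided 0.05 is (1.960 + 0.842) / sqrt(n).

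| Completion | Pairs | Excluded | Detectable change (SD of change) |
|---|---|---|---|
| 30% | 60 | 140 | 0.36 |
| 50% | 100 | 100 | 0.28 |
| 70% | 140 | 60 | 0.24 |
| 90% | 180 | 20 | 0.21 |

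Most patients are lost only if completion is below 50%. Power is not the main issue.

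**4. Illustration of bias.** All values are assumed. Each scenario has 300 runs of 200 patients with 13 two-weekly PHQ-9 scores:

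- mean 14 at baseline, true mean change -5.0 at week 24, with most of the fall early;
- random intercept SD 4, slope SD 4.5 over 24 weeks, residual SD 2.5;
- permanent stopping at a per-visit rate of 1 - c^(1/12) for nominal completion c, either at random or with the log-odds shifted by -0.5, +0.5 or +1.0 for each 5 points by which the last score exceeds its visit mean.

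The all-scores analysis regresses each visit on all earlier ones and fills missing visits by prediction.

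| Completion | Who stops more | Completers | First to last | All scores |
|---|---|---|---|---|
| 30% | random | -4.98 | -3.50 | -4.98 |
| 30% | better | -4.14 | -3.70 | -5.03 |
| 30% | worse, moderate | -5.82 | -3.20 | -4.95 |
| 30% | worse, strong | -6.46 | -2.83 | -5.03 |
| 50% | random | -5.02 | -4.05 | -5.01 |
| 50% | better | -4.38 | -4.14 | -4.96 |
| 50% | worse, moderate | -5.52 | -3.76 | -4.94 |
| 50% | worse, strong | -6.06 | -3.44 | -4.99 |
| 85% | random | -4.98 | -4.73 | -4.98 |
| 85% | better | -4.81 | -4.74 | -4.97 |
| 85% | worse, moderate | -5.11 | -4.64 | -4.96 |
| 85% | worse, strong | -5.37 | -4.47 | -4.98 |

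First-to-last here counts a patient with only a baseline as zero change. Dropping such patients does not remove the shortfall. With random stopping at 50%, a fraction 0.5^(1/12) = 0.944 have a later score, so the mean becomes -4.05 / 0.944 = -4.29.

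**5. Precision.** Under a second set of assumptions (straight-line fall from 14 to 9, 34-42% with a week-24 score), the standard error was 0.59-0.63 for completers and 0.48-0.51 for a repeated-measures analysis. (0.59 / 0.48)^2 = 1.51, equivalent to about 50% more patients. That analysis was given the true covariance, so this is a best case.

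**6. Time point of the secondary scales.** Section 8.3.2 and the Figure 1 note both give 6 months; Section 8.4 gives end of study. Section 3.3 makes end of study a common calendar date after optional continuation, so follow-up length and population would differ. Section 8.3.3 separately lists these scales at both times as exploratory.

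**The case against.** Several stronger readings are tempting, and the documents do not support them.

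- **That only completers are analysed.** The first-versus-last analysis follows in the next sentence, and Section 8.4 adds an exploration of change over time.
- **That most patients are discarded.** No completion rate is given. If 83% were still active and 90% of those answered, 0.83 x 0.90 = 75% would be kept.
- **That the 6-month estimate is biased.** It is unbiased when stopping is unrelated to score, and the direction is otherwise unknown. At 85% nominal completion the illustration stays within about 0.4 points of the truth.
- **That CollaboRATE is a completer-only paired test.** Section 8.3.2 plans to use every available time point; what it lacks is a named method.
- **That the 3-day closure affects all scales.** PAM-13, WSAS and CollaboRATE stay open for 30 days. PAM-13 and WSAS have two scores to 6 months, so a repeated-measures model adds little for them.
- **That the secondary time point is undecided.** Two places say 6 months, so the phrase in Section 8.4 is mainly wording to align.

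It is also fair to say that the illustration favours the proposed method: stopping depends on an observed score, so missing at random holds by construction, and no other case was run. The first-to-last shortfall also depends on the assumed course; with a plateau by week 8 and lighter random stopping it shrinks to about -4.8. Nor does the plan call first-versus-last a 6-month result. Finally, the loss of the week-22 patient is inferred, because 3 days is how long the questionnaire is open and no analysis window is stated.

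What still stands is that the named test ignores the intermediate scores, the back-up estimates something else, and no missing-data assumption is given.

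**Conclusion.** The point holds at modest severity. From the text alone, the fixed-time change in the three app scales rests on patients with both scores, the end score must be given within a 3-day opening, and the back-up does not estimate a 6-month change.

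The size is illustrative. Across 30% to 85% nominal completion, completer estimates of a true -5.0 ran from -4.1 to -6.5 and first-to-last from -2.8 to -4.7, while an analysis of all scores stayed between -4.9 and -5.0. These figures rest on assumed completion, variances, course and stopping mechanism, and on missing at random.

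The primary endpoint is untouched. The outcomes are mainly exploratory and come from one uncontrolled group, although Section 8.4 also names the paired t test for PHQ-9 change within its paragraph on primary and secondary testing. The change is still worth making, because a better method is available for data already in hand.

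**What to change.** In Sections 8.3.3 and 8.4:

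1. Make the main analysis of PHQ-9, WHO-5 and PDQ-D5 a mixed model for repeated measures on all scheduled scores to week 24, from every enrolled patient with a baseline, with the baseline as one of the repeated outcomes. Measure time from enrolment and report the week-24 change with a 95% CI.
2. State the missing-at-random assumption and a fallback covariance structure. Thirteen visits give 13 x 14 / 2 = 91 unstructured parameters, which may be too many for 200 patients.
3. Keep the completer paired t test as a sensitivity analysis, and describe first-versus-last as change to last available score.
4. Name the same model for CollaboRATE (baseline, Day 84, 6 months).
5. Align the end-of-study wording in Section 8.4 with the 6-month secondary time point in Sections 3.2 and 8.3.2, and say which two of the three listed time points Section 8.3.3 means.

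The cost is SAP wording and routine programming, with no new data. The downside is reliance on missing at random: if patients stop for reasons that their recorded scores do not show, the model does not protect against bias.
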